**D.2.a. Questions for Patients in Both Groups after Consenting and Eye Exam**

Are you aware that glaucoma can be treated with laser therapy instead of eye drops?  
Did you know that laser therapy is a possible first option for treating glaucoma before eye drops?  
Did you discuss laser therapy with your glaucoma doctor today?  
Would you consider having laser treatment? Why or why not?  
Would you consider having this laser therapy instead of filling your prescription for eye drops?  
If no, please describe reasons.

**D.2.b. Questions for Intervention Patients After Viewing the Presentation and Video**

Did you have any questions about the educational program we showed you?  
Would you consider having laser therapy to treat your glaucoma?  
Would you consider having this laser therapy instead of filling your prescription for eye drops?  
If no or maybe, let's discuss why?  
If yes, can I help you to schedule a laser appointment at your convenience?

In order to assess the beliefs and attitudes of a group of ophthalmologists about SLT as first line therapy before and after viewing Educational Intervention, we will ask the following questions to determine how they approach newly diagnosed patients with glaucoma.

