## **D.1 Data Management and Analysis**

**D.1.a. Assessment Measures:** The primary outcome measure is the number of patients who complete an SLT over the study period. Rates of SLT procedures will be compared between patients enrolled in the SLT Educational Intervention group versus the Usual Care group. Rates of SLT will be tracked in each group after patients are asked the first set of questions and after the Intervention group is shown the video. Follow-up eye exam appointments for patients in both groups will be tracked for a 6-month period to assess the number of patients who elect to have SLT.

The secondary outcome is to assess the beliefs and attitudes of patients and a group of ophthalmologists about SLT as first line therapy before and after viewing Educational Intervention. The research coordinator will ask all patients questions about their knowledge, beliefs, barriers, and attitudes about SLT vs. medication as first line treatment of glaucoma. These questions will be developed with [name], a psychologist and vision researcher at Sidney Kimmel Medical College with extensive experience in survey development and sampling techniques. She will be consulted during the development phase to revise and implement the following questions. If a more understandable explanation of the risks/benefits of SLT versus medications results in a significant increase in SLT treatments, that suggests that the real barrier is patient understanding and perhaps to a lesser extent physician education.

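### Patient attitude after the education is measured in the Intervention arm only, so the patient survey result is an uncontrolled change within one session

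*Combined protocol and SAP*

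**What the plan says.** Section D.1.a sets the outcome: "The secondary outcome is to assess the beliefs and attitudes of patients and a group of ophthalmologists about SLT as first line therapy". The same sentence fixes the timing, with one reading on either side of the education. It adds: "The research coordinator will ask all patients questions about their knowledge, beliefs, barriers, and attitudes about SLT vs. medication as first line treatment of glaucoma".

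Two patient lists follow. D.2.a is headed "Questions for Patients in Both Groups after Consenting and Eye Exam" and D.2.b is headed "Questions for Intervention Patients After Viewing the Presentation and Video". Section C.4 gives the same picture: Intervention patients answer D.2.a, see the presentation and answer D.2.b, while Usual Care patients answer D.2.a only.

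D.2.a contains two awareness items, one of them "Did you know that laser therapy is a possible first option for treating glaucoma before eye drops". Its closing prompt is "If no, please describe reasons". The matching prompt in D.2.b is "If no or maybe, let's discuss why", and the next line offers help with booking. Neither list states response options. Section F names one survey analysis, Fisher's exact test of answers before against after the education. It gives no between-arm survey comparison.

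**The concern.** A rise in willingness between the two lists would be read as an effect of the education. Other explanations would produce the same rise: being asked the same thing twice within one visit, wanting to please the person running the session, or a different way of recording undecided answers. A control reading taken at the same point would separate the first of these from the education and give some gauge of the second. The randomised Usual Care patients are already sitting with the coordinator, but are not asked again.

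Knowledge is in a weaker position. It is among the things to be asked of all patients, yet neither awareness item is put to anyone after the education. D.1.a would interpret an increase in SLT as pointing to patient understanding as the barrier, but no planned measurement shows whether understanding changed.

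**Working it through.** The plan gives no effect size, power or expected response rate for the survey, so there is no stated figure to reproduce. The check is mainly a comparison of the texts.

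**1. Order of steps (Section C.4)**

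- Intervention: eye exam and physician discussion; D.2.a; presentation; D.2.b, ending with the booking offer; time for questions to the coordinator.
- Usual Care: eye exam and physician discussion; time for questions to the coordinator; D.2.a; no further questions.

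**2. Items in the two lists (six lines in D.2.a, five in D.2.b)**

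| Content | D.2.a | D.2.b | Match |
|---|---|---|---|
| Awareness, two items | yes | no | 0 of 2 repeated |
| Laser discussed with doctor today | yes | no | not applicable |
| Would consider laser | yes | yes | near-identical |
| Laser in place of the eye-drop prescription | yes | yes | word for word |
| Follow-up prompt | *no* only | *no* or *maybe* | differs |
| Questions about the programme; booking offer | no | yes | not applicable |

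Attitude therefore has one exact and one near-exact pair. Knowledge has none.

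**3. Comparisons these data allow**

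- D.2.a against D.2.a, between arms: randomised, but taken before the Intervention arm sees anything, so it cannot show an effect of the presentation.
- D.2.a against D.2.b, within the Intervention arm: the planned comparison; at most 20 patients and no control.
- Intervention D.2.b against Usual Care D.2.a on the identical item: randomised, but not planned and not like for like. One arm answers a repeated question, and coordinator question time comes before the reading in Usual Care but after it in the Intervention arm.

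**4. Why a coding rule is needed (hypothetical counts)**

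Suppose 8 of 20 say yes before, and afterwards 8 say yes, 8 maybe and 4 no.

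- *Maybe* counted as not-yes: 8/20 against 8/20, Fisher p = 1.0.
- *Maybe* counted as yes: 8/20 against (8 + 8)/20 = 16/20, Fisher p = 0.022.

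The counts are invented. They show that an unstated rule could decide the result; they do not estimate any bias in this trial.

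**5. What a between-arm reading could deliver**

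With 20 per arm (Section C.3) and an assumed 50% yes in each arm, the 95% interval half-width is 1.96 × √(0.5×0.5/20 + 0.5×0.5/20) = 1.96 × 0.158 = 0.31, or 31 percentage points.

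Exact Fisher power at 20 per arm (two-sided 0.05, assumed rates), with the number per arm for 80% power (normal approximation with continuity correction):

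| Assumed yes rates | Power | Per arm for 80% |
|---|---|---|
| 20% vs 50% | 41% | 45 |
| 30% vs 60% | 35% | 49 |
| 20% vs 60% | 65% | 28 |
| 30% vs 70% | 60% | 29 |

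At this size the comparison is an estimate, not a confirmatory test.

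**The case against.** The strongest defence is that the plan does what it says. D.1.a defines the secondary outcome as before and after viewing, and Usual Care never views the education. The hypothesis is about selecting SLT, which is the primary outcome and is compared between randomised arms. The study is a pilot of 40, and a survey psychologist is to revise the questions. All of this is correct. It makes the point an improvement to a secondary outcome, not a breach of a promise. But revising item wording would not by itself give Usual Care a second reading.

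Three stronger readings are tempting, and the documents do not support them.

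- A reader might infer that nothing comparable is asked before and after. That fails for attitude: one item is word for word the same and another nearly so.
- A reader might infer that a *maybe* category is added after viewing and creates an artefact that can be sized. Neither list gives a response scale; *maybe* appears only in a conversational prompt, and D.2.a does not exclude it. What stands is that the options are undefined and the prompts differ.
- A reader might infer that no randomised comparison can be made. None is planned, but Intervention D.2.b could be set against Usual Care D.2.a on the identical item, with the flaws shown in the working.

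Two objections to the remedy also have force. Repeating the awareness items would not measure knowledge, because each states its own answer and would probably be near ceiling minutes later. And asking Usual Care about laser twice could slightly prompt SLT uptake in the control arm.

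**Conclusion.** The point holds, within limits. Post-education attitude is read in one arm only, on one identical and one near-identical item with undefined response options, and knowledge has no post-viewing measure in either arm. As planned, the patient part of the secondary outcome is an uncontrolled change within one session in at most 20 patients. It cannot be attributed to the education.

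No numerical size can be given to the bias: that would need response options and answer patterns the documents do not state. The conclusion rests on the order of steps in C.4, the two lists as printed, and Section F as the only survey analysis. It does not touch the randomised comparison of SLT uptake. The change is advisable but not essential to the trial's main question.

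**What to change.** Put the two willingness items to both arms at the end of the coordinator session: after the presentation in the Intervention arm, and at the close of the session in Usual Care. Use the same wording and the same fixed yes/no/maybe options in D.2.a and at the end. Record the answers before any discussion of reasons or scheduling.

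In Section F, make the between-arm difference in end-of-session answers the patient attitude result, with a confidence interval and a stated rule for *maybe*. Report the within-Intervention change as descriptive; if it is tested at all, use a paired method, since the same patients answer twice. Do not present repeated awareness items as a knowledge measure. Without a different instrument, state that knowledge after the education is not assessed.

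The cost is protocol wording, a one-page form and a few minutes for each of the 20 Usual Care patients. The downside is a second prompt about laser in Usual Care, which could slightly raise SLT uptake there and so narrow the primary contrast. The Intervention arm already receives that second prompt.

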**D.2.c. Ophthalmologists' Questions Before Viewing the Presentation and Video:**

- 1) What treatment options do you currently offer your newly diagnosed glaucoma patients?
- 2) What is your preferred treatment for newly diagnosed glaucoma patients? Why?
- 3) What percentage of your newly diagnosed glaucoma patients receive SLT? Why?
- 4) Where do you see SLT in the glaucoma treatment paradigm?
- 5) Would you use SLT as first line therapy for all/most of your newly diagnosed POAG patients?  
If yes, why?  
If no, what would persuade you to use SLT more frequently?

**D.2.d. Ophthalmologists' Questions After Viewing the Presentation and Video:**

- 1) Did this educational program convince you that SLT is appropriate as first line therapy instead of medication? Why or why not?
- 2) If you are reluctant to recommend SLT as first line therapy, please explain why.
- 3) What additional information would you like to know to help make an informed decision?

**E. Study Timeline:** The study will be conducted between July 1, 2017 and June 31, 2018. We will complete all IRB submission and staff training prior to July 1, 2017. We will develop the Educational Intervention and video during the initial 3 months of funding period. We will identify, recruit, consent and enroll 40 patients, who will be randomized, 20 to the Educational Intervention group and 20 to the Usual Care group between August 1, 2017 and January 30, 2018. Data cleaning, analysis, and dissemination of findings will be completed by June 30, 2018 and a dissemination plan will be implemented to include submitting publication and

abstracts for presentations at national research meetings such as American Glaucoma Society and American Academy of Ophthalmology.

**F. Statistical Analysis:** All data analyses will be conducted using R (R core team, Vienna, Austria). Fisher's exact test for count data will be used to compare the pre- and post-SLT Educational Intervention survey answers. Descriptive statistics will be used to present patient demographic and clinical data.

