**AIM 3:** Assess the beliefs and attitudes of a group of ophthalmologists about SLT as first line therapy before and after viewing the Educational Intervention.

**Hypothesis:** *Better informed patients and ophthalmologists tend to select SLT in place of ocular medications as either first line or in place of medications after initially using medications.*

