**C.5. Tracking Outcomes:** The goal of Aim 1 is to determine if the SLT Educational Intervention used by the research coordinator and physicians with patients could lead to greater utilization of SLT by patients. Rates of SLT will be tracked in each group after patients are asked the first set of questions and after the Intervention group is shown the video. Follow-up eye exam appointments for patients in both groups will be tracked for a 6-month period to

assess the number of patients who elect to have SLT. The rate of SLT will be compared between the SLT Educational Intervention group and the Usual Care group at these time periods.

Patients will provide their name and date of birth on the consent form, both of which will be used to extract and de-identify data from their electronic medical record, including demographics, disease severity, and prior and current glaucoma treatments. Demographic data will include race/ethnicity, gender, and age.

**C.6. Assess Ophthalmologists' Beliefs and Attitudes about Laser (AIM 3):** A total of 15 glaucoma specialists and 20 general ophthalmologists will be interviewed by the research coordinator via telephone or in person. These ophthalmologists will be recruited from the Wills Eye Hospital Glaucoma Service, Wills Eye Hospital Primary Eye Care Service, Wills Eye Medical Staff, community ophthalmologists affiliated with Wills Eye Hospital, and other ophthalmologists as needed. We will recruit these ophthalmologists by asking for their input in helping patients make informed decisions about glaucoma treatment and management and assess how they approach patients with glaucoma.

These ophthalmologists, who will be asked to fill out a survey, will be considered study subjects and will be requested to sign an informed consent form prior to participation. After obtaining informed consent, we will request their input to answer several questions over the phone. Once they agree to participate and complete the phone screening questions, the research coordinator will send them a link to the Powerpoint slides including the video, and request they complete a survey (survey monkey) after viewing the intervention (See Section D.2.c).

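### As headed, the ophthalmologists' before and after question sets share no item, so Aim 3 has no same-item change to calculate, and the planned Fisher's exact test ignores pairing wherever an item is repeated

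*Combined protocol and SAP*

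**What the plan says.** Section B gives Aim 3 as: "Assess the beliefs and attitudes of a group of ophthalmologists about SLT as first line therapy before and after viewing the Educational Intervention". Section D.1.a makes this part of the secondary outcome, in these words: "assess the beliefs and attitudes of patients and a group of ophthalmologists about SLT as first line therapy before and after viewing Educational Intervention". At the end of D.2.b, the paragraph that introduces the ophthalmologist questions says that "we will ask the following questions to determine how they approach newly diagnosed patients with glaucoma".

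D.2.c is headed as the set asked before viewing. It has five numbered items: options offered, preferred treatment, percentage of new patients receiving SLT, the place of SLT in treatment, and "Would you use SLT as first line therapy for all/most of your newly diagnosed POAG patients", with the follow-up "If no, what would persuade you to use SLT more frequently".

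D.2.d is headed as the set asked after viewing. It has three items: "Did this educational program convince you that SLT is appropriate as first line therapy instead of medication" (with a request for reasons), an explanation from anyone still reluctant, and what further information is wanted.

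Section C.6 sets the sequence for 15 glaucoma specialists and 20 general ophthalmologists. "Once they agree to participate and complete the phone screening questions", the coordinator sends the link to the slides and video and will "request they complete a survey (survey monkey) after viewing the intervention (See Section D.2.c"). C.6 names no section for the phone questions and never cites D.2.d.

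Section F names Fisher's exact test for comparing pre- and post-intervention survey answers. It does not say whether this covers patients, ophthalmologists or both, and it names no paired method.

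**The concern.** A before-and-after assessment of attitude needs at least one question asked in the same form at both times. If none is, the before/after part of Aim 3 rests on asking ophthalmologists whether the program convinced them. That is a leading self-report, and it is awkward to read for someone who favoured SLT already.

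The cross-reference in C.6 adds a practical risk: a coordinator following C.6 and one following the headings would send different post-viewing surveys. A baseline answer not collected before viewing cannot be recovered afterwards.

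Where an item is repeated, a test for two independent groups discards the information on who changed their answer and can miss a shift that the paired data would show.

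**Working it through.** **Step 1. Item comparison for ophthalmologists.** Number of people: 15 + 20 = 35 (C.6).

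| Topic | D.2.c (before) | D.2.d (after) |
|---|---|---|
| Options currently offered | item 1 | none |
| Preferred treatment | item 2 | none |
| Percentage receiving SLT | item 3 | none |
| Place of SLT | item 4 | none |
| Would use SLT first line | item 5 | related in topic only: items 1 and 2 |
| What would persuade / what more is wanted | follow-up to item 5 | related in topic only: item 3 |

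Items with the same wording: 0. The nearest pair is D.2.c item 5 and D.2.d item 1. Cross-tabulating them gives the proportion calling themselves convinced among those who first said no, which is not a change in a measured answer.

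**Step 2. The cross-reference.** C.6 runs phone questions, then link, then survey. That order fits the headings if the survey is D.2.d. The citation of D.2.c contradicts the D.2.c heading. C.6, D.2.c and D.2.d cannot all stand as written.

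**Step 3. Item comparison for patients.** D.2.a and D.2.b share one item verbatim: whether the patient would have laser rather than fill the eye-drop prescription. The 20 Intervention patients are asked it twice, so the pairing problem already exists there.

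**Step 4. What ignoring pairing costs.** The documents give no significance level and no expected answers, so there is no plan figure to reproduce. Assumptions: two-sided 0.05, and answers coded yes/no.

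Exact McNemar with k switches all in one direction: p = 2 × 0.5^k.
- k = 5: 2 × 0.03125 = 0.0625
- k = 6: 2 × 0.015625 = 0.031

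Fisher's exact test, two-sided, on the before row (a yes, 35 − a no) and the after row (a + 6 yes, 29 − a no):

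| Initial yes, a | Fisher p |
|---|---|
| 0 or 29 | 0.025 |
| 1 or 28 | 0.055 |
| 5 | 0.154 |
| 10 | 0.216 |
| 14 | 0.232 |

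So six one-way switches out of 35 (6/35 = 17%) pass the paired test at any baseline. They fail Fisher's test for every baseline from 1 to 28.

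**Step 5. Reverse switches.** Take yes answers rising from 12/35 to 19/35. Fisher gives p = 0.148 whatever the pairing. Exact McNemar depends on who moved:

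| Switches to yes / to no | McNemar p |
|---|---|
| 7 / 0 | 0.016 |
| 8 / 1 | 0.039 |
| 9 / 2 | 0.065 |
| 12 / 5 | 0.143 |
| 15 / 8 | 0.210 |

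The gain from pairing is large when people mostly keep their answer or move one way. It has almost gone at 12 against 5, and at 15 against 8 McNemar gives the larger p-value.

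**The case against.** Several points on the other side have force.

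- D.2.d is not silent on attitude. Its second item asks reluctant ophthalmologists to explain themselves, and the first asks for reasons, which would often separate those not convinced from those who needed no convincing. This stands: there is some post-viewing information on stance, but in free text and in a different form from the baseline question.
- Aim 3 says assess, not estimate a change, and this is a pilot with mostly open questions. That is fair, but Section F does plan a formal comparison of pre and post answers.
- The citation in C.6 is most simply a one-letter slip. I agree. A reader might infer from it that all five D.2.c items are asked at both times, so that change is measurable after all. No section says so; that reading takes C.6 literally for the survey and the heading literally for the phone call.
- The ophthalmologist p-values describe repeated answers that the plan, as headed, would not collect. That is true. They show what would follow if items were repeated; the patient item is where the test is already unsuitable.
- D.1.a says the questions will be revised during development. It does not commit to repeating any of them.

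A reader might also infer that Fisher's test would give false positive results. When a person's two answers are positively correlated, the main effect is the opposite: lost power.

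**Conclusion.** The point holds for Aim 3 and for the survey analysis. On the headings, no same-item change can be calculated for any of the 35 ophthalmologists, and C.6 conflicts with the heading of D.2.c. The planned test does not suit answers from the same person, which affects one patient item now and would affect any ophthalmologist item that is repeated.

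The size of the power loss depends on the pattern of switching, which the documents do not give. The figures rest on an assumed two-sided 0.05 level and yes/no coding, and they do not show that a paired test always gives the smaller p-value.

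Nothing here touches the randomized comparison of completed SLT, which is the primary outcome. This should be changed, but it is not a flaw in the trial's main result.

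**What to change.** 1. Repeat at least D.2.c item 5, and preferably item 2, in the post-viewing survey, with identical wording and closed answer options at both times. Keep the requests for reasons as free text, and keep D.2.d items 1 to 3 as feedback on the program.
2. Correct C.6 so that it names which set is asked by phone or in person and which is in the online survey, consistent with the headings of D.2.c and D.2.d.
3. In Section F, use exact McNemar for every repeated yes/no item, including the patient item shared by D.2.a and D.2.b, with a stated rule for maybe answers. Show a before-by-after table for any repeated item with more than two categories. Keep Fisher's exact test for comparisons between groups, and say which respondents each test covers.
4. Report the before/after changes as uncontrolled. For ophthalmologists, add that the mode differs: telephone or in person before, online after.

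The cost is one or two extra survey questions, a few minutes per respondent, some work to define the closed options, one corrected citation and one changed test. Patient procedures stay as they are. The repeated items would support a description of change and a paired test, but not attribution to the program alone.

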### **C.3. Recruitment and Inclusion Criteria:**

**Patients:** A total of 40 patients will be recruited from the Wills Eye Hospital Glaucoma Care Specialists' private practice and the resident-run Glaucoma Clinic over an 6-month period for this pilot study. Eligible patients will be between 40 and 90 years of age, and have either high-risk ocular hypertension, primary open-angle glaucoma, or pseudo-exfoliation glaucoma with no previous laser trabeculoplasty. Eligible patients will be naive to medication and laser **or** currently being treated with glaucoma eye drop(s). Only patients within three years of a glaucoma-related diagnosis and stable intraocular pressure will be invited to participate.

After IRB approval, the patients' electronic medical records will be reviewed in advance of their next scheduled eye exam. Eligible patients will be invited to participate in the study by letter and/or telephone call, in advance of their scheduled appointment. Eligible patients may also be approached by our study team when checking in on the same day of their eye exam appointment.

All patients will be asked to provide written informed consent, prior to meeting with their ophthalmologist. Once patients are consented, a yellow-colored page with large font (**Patient Enrolled: SLT vs. Meds Study**) will be inserted into the patient's medical chart folder to alert the doctor that the patient is enrolled in the study and that both treatment options should be discussed in detail.

Those enrolled will be randomized to either the SLT Educational Intervention group (n=20) or the Usual Care group (n=20). The knowledge, beliefs, barriers, and attitudes about SLT vs. medication as first line treatment of glaucoma will be assessed in both groups.

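### If the 6-month tracking runs from each patient's enrolment, enrolment to January 30, 2018 cannot be reconciled with completing the analysis by June 30, 2018, and no data cut or short-follow-up rule is given

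*Combined protocol and SAP*

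**What the plan says.** Section C.3 sets recruitment "over an 6-month period for this pilot study". Section E dates it, with 40 patients randomised "20 to the Educational Intervention group and 20 to the Usual Care group between August 1, 2017 and January 30, 2018". Section E also places development of the educational material and video in the first 3 months of funding.

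Section D.1.a defines the outcome: "The primary outcome measure is the number of patients who complete an SLT over the study period". It then describes the observation period: "Follow-up eye exam appointments for patients in both groups will be tracked for a 6-month period". Section C.5 has the same 6-month tracking and adds that "The rate of SLT will be compared between the SLT Educational Intervention group and the Usual Care group at these time periods", meaning after the first questions, after the video and over follow-up. Neither section says when the 6 months start.

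On completion, Section E says "Data cleaning, analysis, and dissemination of findings will be completed by June 30, 2018". Section F (Statistical Analysis) does not mention a data cut or incomplete follow-up.

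**The concern.** The primary outcome counts events that accumulate over follow-up, so the plan has to say how long each patient is observed and its calendar has to allow that time. On the natural reading, recruitment and follow-up together need 12 months from August 1, 2017. Section E allows 11, and cleaning, analysis and dissemination must fit inside those 11.

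If the dates are followed and enrolment uses its full window, later enrolees are observed for less than 6 months. The analyst would then have to decide, possibly with data in hand, whether to count them as they stand, exclude them or wait. The SLT rates taken straight after the first questions and after the video are not affected.

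**Working it through.** **Inputs.** Enrolment August 1, 2017 to January 30, 2018 (Section E); follow-up 6 months (C.5, D.1.a); completion June 30, 2018 (E); 40 patients (C.3, E). Accrual pattern, analysis time and SLT uptake are not given, so they are assumed below.

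**The plan's own figure.** August 1 to January 30 inclusive is 183 days, so the 6-month recruitment period reproduces. The June 30 completion date does not:

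- Required: January 30 + 6 months = July 30, 2018.
- Allowed: June 30, 2018, which is 30 days earlier.
- A patient enrolled on January 30 has 151 days (5.0 months) by June 30.
- The last enrolment that reaches 6 calendar months by June 30 is December 30–31, 2017. With one month reserved for analysis it is November 30; with two, October 31.

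**Common-close reading.** If everyone is counted to June 30, follow-up runs from 151 days (enrolled January 30) to 333 days (enrolled August 1), or about 5 to 11 months.

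**Patients short of 6 months, uniform accrual from August 1 (assumed).** Patients short = 40 × (late enrolment days ÷ 183).

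- Cut June 30: January 1–30 = 30 days; 40 × 30/183 = 6.6.
- Cut May 31: December 1–January 30 = 61 days; 40 × 61/183 = 13.3.
- Cut April 30: November 1–January 30 = 91 days; 40 × 91/183 = 19.9.

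**Follow-up time lost.** Add up the days by which each enrolment day falls short and divide by the total planned follow-up over the 183 enrolment days (33,270 days, about 182 each): 465/33,270 = 1.4%; 1,860/33,270 = 5.6%; 4,216/33,270 = 12.7%.

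**Expected SLTs missed.** With a constant hazard and six-month uptake p (both assumed), a patient with full window L and observed time F has probability (1−p)^(F/L) − (1−p) of an SLT inside 6 months but after the cut. For the January 30 enrolee at a June 30 cut with p = 0.5, this is 0.5^(151/181) − 0.5 = 0.061. Averaging over enrolment days and multiplying by 40 gives the last column for p from 0.1 to 0.5.

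| Time reserved for analysis | Patients short, of 40 | Follow-up lost | SLTs missed |
|---|---|---|---|
| None | 6.6 | 1.4% | 0.05–0.2 |
| One month | 13.3 | 5.6% | 0.2–0.8 |
| Two months | 19.9 | 12.7% | 0.5–2.0 |

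**Later effective start.** If funding starts July 1, 2017 (assumed), development runs to the end of September. Enrolment from October 1 to January 30 covers 122 days. The late days are unchanged, so the patient counts scale by 183/122 = 1.5: 40 × 30/122 = 9.8, 40 × 61/122 = 20.0 and 40 × 91/122 = 29.8.

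**Other accrual shapes, June 30 cut, start August 1.** Rate falling linearly to zero: 40 × (30/183)² = 1.1 patients. Rate rising linearly from zero: 40 × [1 − (153/183)²] = 12.0. If the 40th patient enrols by December 30–31, none fall short, but no analysis time is left.

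**The case against.** The documents do not say that the 6 months run per patient, and D.1.a words the primary outcome over the study period. A reader might infer from the dates that January enrolees simply cannot complete follow-up. That is too strong, because it holds only on the per-patient reading. The common-close reading removes the clash for the primary outcome, but it does not rescue the plan: follow-up would be unequal, would not be 6 months, and would still need a close date that the text does not give. Starting a shared 6-month period when enrolment closes would also end on July 30.

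The size of the effect can also be overread. Each SLT is 5 percentage points of an arm's rate (1/20), and a reader might infer that the arm comparison is distorted by that much. With no analysis time the expected loss is well under one SLT across both arms. Randomisation should roughly balance entry dates, so the documents support no claim that either arm is favoured. This is also a self-described pilot. In the other direction, zero analysis time is a lower bound, because Section E puts all cleaning, analysis and dissemination before June 30.

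Two further limits stand. Some pages were not available to this review, so the missing data cut and short-follow-up rule are established only for the available text. The impossible end date in Section E ("The study will be conducted between July 1, 2017 and June 31, 2018") is a slip and adds nothing to the point.

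**Conclusion.** The concern holds conditionally. On the natural per-patient reading, Section E's completion date is incompatible with the plan's own enrolment and follow-up periods by 30 days before any analysis time. On the common-close reading, the stated 6-month period is not what patients would receive. Either way the observation window for the primary outcome needs to be defined.

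The effect is small to moderate. Under uniform accrual from August 1, about 7 to 20 of 40 patients are short, depending on whether zero to two months are kept for analysis. From October 1 the figures are about 10 to 30. Expected SLTs missed, for an August 1 start, run from about 0.05 to 2.0. These figures rest on assumed accrual, uptake of 10–50%, a constant hazard and assumed analysis time; the documents give no time-to-SLT data. The date arithmetic itself rests only on the stated dates and the reading of the 6 months. No direction of bias can be stated. This should be fixed before analysis, but it does not undermine the trial.

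**What to change.** 1. In D.1.a, define the primary outcome as SLT completed within 6 months of randomisation, with the same window for every patient, and align C.5 with it.
2. In Section E, set the data cut no earlier than 6 months after the last enrolment (July 30, 2018 on current dates), schedule cleaning and analysis after it, and correct the end date.
3. If June 30, 2018 cannot move, use one shorter common window that every patient can complete before the cut: at most 151 days less analysis time, for example 151 − 30 = 121 days with a May 31 cut.

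The cost is a change of wording and a later chart pull. Under items 1 and 2, results come at least a month later plus analysis time. Under item 3, SLTs done after the shorter window are not counted. Closing enrolment by December 30 instead would, at a uniform pace from August 1, yield about 40 × 152/183 = 33 patients and still leave no analysis time.
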